5.2.2.3. Bayesian Estimation of Dose Response Models

The Bayesian estimation of the E_{max} model uses prior distributions on the placebo response (E₀), the dose that produces half the maximal drug effect (ED₅₀), E_{max} parameters, and the β loading dose parameter, if it is included.

The specification of the E_{max} model and the prior distributions for some of its parameters are based on three meta-analyses of clinical dose response from more than 100 compounds.^{7,8,9} The E_{max} model specification is also supported by data from another compound with similar target biology, for which dose finding studies were performed in three indications.

We will use a *t* prior distribution for the logit of the placebo response centered at logit(0.05). A prior scale parameter (analogous to the standard deviation) of 4.0 (logistic scale) will be used, which yields a diffuse prior distribution for the placebo response. A *t* prior distribution for the E_{max} parameter is used, which is also specified on the logistic scale. It is centered at 0. This prior distribution will also be diffuse on the logistic scale with a prior scale parameter of 4.0. If a loading dose effect is included, its *t* prior distribution will also be centered at 0 with a prior scale parameter of 4.0. Our current projected value for the ED₅₀ is P₅₀=30 mg. The prior distribution for the ED₅₀ is derived from a *t* prior distribution for the normalized parameter, log(ED₅₀/ P₅₀). The *t* distribution for log(ED₅₀/ P₅₀) is centered at 0 with scale parameter, 1.73. This is the recommended distribution derived from the meta-analyses, and implemented in the R package, clinDR. It implies the ED₅₀ is likely to be within 30-fold of its initial projected value (P₅₀). The degrees of freedom (df) for each prior *t*-distribution is 5, also obtained from the meta-analyses of dose response data.

5.2.3. Continuous Endpoints

For continuous secondary endpoints up to Week 24, a mixed-effect model with repeated measures (MMRM) will be used. This model will include the factors (fixed effects) for treatment group, visit, treatment-by-visit interaction, and relevant baseline value when

modeling the change from baseline. Within the framework of MMRM, the treatment difference will be tested at each time point. Visit will be modeled as a categorical covariate. Unstructured covariance matrix will be assumed for the model errors.

When modeling the change from baseline values, the variable for visit will start with the first post-baseline visit, and the actual baseline value will be included as a covariate. At each visit, estimates of least square mean (LSM) values and the LSM differences between the PF-06651600-treated groups and the placebo group will be derived from the model. The corresponding p-values, standard errors and 95% CIs will also be derived from the model. Estimates of the difference in LSMs along with the two-sided 95% CI will also be provided for the treatment groups versus placebo group for the initial 24 weeks.

Exploratory endpoints will be summarized using descriptive statistics unless specified otherwise.

The MMRM method described above will also be applied to the continuous data up to Week 48 (over the entire study) for initial active treatment groups. LSM, standard error and 95% CI will be presented for each treatment group without treatment comparison. Descriptive statistics based on the observed case data will also be provided from baseline to Week 48 by 7 treatment sequences ([Figure 1](#)), without combining two placebo groups, as supportive.

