### **9.2.3. Analysis of Secondary Endpoints**

For all regions, analyses of secondary endpoints that are not  $\alpha$  controlled will use the approach outlined below.

Secondary endpoints that are binary variables will be analyzed using the same approach as Analysis 1 in [Table 6](#).

For continuous endpoints, a mixed-effects model with repeated measures (MMRM) will be used. This model will include the factors (fixed effects) for treatment group, visit, treatment-by-visit interaction, and relevant baseline value when modeling change from baseline. Within the framework of MMRM, the treatment difference will be tested at each time point.

All secondary endpoints will be evaluated at the 5% level of significance, without adjustment for multiple comparisons.

Details on the analysis of individual secondary endpoints will be provided in the SAP.

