6.2.10. Alopecia Areata Patient Priority Outcomes (AAPPO) Scale

AAPPO was measured at baseline, Weeks 4, 8, 12, 18, 24, 34, 40, and 48. Endpoints include:

- Current hair loss on scalp, eyebrows, eyelash, and body hair (Items 1-4) for each individual item scored as 0='no hair loss', 1='little hair loss' and 2-4='moderate-complete hair loss'.
- Improvement on AAPPO items 1-4 among participants with a baseline score 2-4 indicating moderate-complete hair loss who achieved a score of 0='no hair loss' or 1='little hair loss'.
- Change from baseline in AAPPO Emotional Symptoms domain score, where Emotional Symptoms domain score is defined as mean of items 5-8.
- Change from baseline in AAPPO Activity Limitations subscore, where Activity Limitations subscore is defined as mean of items 9-11.
- Population: FAS.
- Statistical Methods:
 - MN for Proportion of patients with Improvement on Items 1-4. A descriptive summary of the distribution of subjects according to each category of AAPPO Items 1-4 will be provided.
 - MMRM for change from baseline in AAPPO Emotional Symptoms and Activity Limitations up to week 24. MMRM for initial active treatment groups for entire duration. Descriptive statistics for all treatment groups over the entire duration.
 - Missing Data: Exclude missing due to COVID-19, consider missing due to other as non-responders. For change from baseline, missing values are handled in the MMRM model. Observed Cases will be used for the descriptive analysis.

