6.3.8. Change From Baseline in the Depression Subscale Score of HADS

- Change from baseline in the depression subscale score of the HADS at Weeks 4, 8, 12, 24, and 48.
- Population: FAS.
- Statistical Method: MMRM up to week 24. MMRM for initial active treatment groups for entire duration. Descriptive statistics for all treatment groups over the entire duration.
- Missing Data: handled in MMRM model. Observed Cases will be used for the descriptive analysis.

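### The MMRM for change from baseline has no baseline-by-visit term, so Week 24 contrasts may lose some precision and are not assured to be unbiased if dropout depends on baseline differently by arm

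*SAP*

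**What the plan says.** SAP 5.2.3 describes the MMRM for continuous secondary endpoints up to Week 24: "This model will include the factors (fixed effects) for treatment group, visit, treatment-by-visit interaction, and relevant baseline value". It adds that "the actual baseline value will be included as a covariate", that "Visit will be modeled as a categorical covariate", and that "Unstructured covariance matrix will be assumed for the model errors". Protocol 9.2.3 gives the same fixed effects, ending in "treatment-by-visit interaction, and relevant baseline value when modeling change from baseline".

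The endpoint sections add no model terms:

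- Change in SALT score (SAP 6.2.6) simply names MMRM.
- SAP 6.2.10 specifies "MMRM for change from baseline in AAPPO Emotional Symptoms and Activity Limitations up to week 24", with the visit schedule "AAPPO was measured at baseline, Weeks 4, 8, 12, 18, 24, 34, 40, and 48".
- SAP 6.3.8 covers "Change from baseline in the depression subscale score of the HADS at Weeks 4, 8, 12, 24, and 48" by MMRM, and SAP 6.3.9 does the same for anxiety. The HADS endpoints are secondary only for the EMA and VHP authorities.

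SAP 5.3.2 leaves missing values unimputed, assumes MAR, and states without qualification that the model gives unbiased estimates and valid inference under MAR.

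**The concern.** Both documents write out the treatment-by-visit interaction and name no matching interaction for baseline, so the natural reading is a single baseline coefficient. Means are free at every visit and the covariance is unstructured. Only the baseline slope is held constant, and no reason is given.

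The slope of change on baseline depends on how strongly each visit still correlates with baseline and on the SD at that visit. If the correlation decays from Week 4 to Week 24 without an offsetting rise in SD, the slope steepens. A shared slope then sits between the early and late values, and some baseline variation stays in the Week 24 residual. The standard error of the Week 24 contrast becomes larger than it need be.

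The second stake is validity under dropout. Likelihood inference under MAR relies on a correct mean model. If completers differ between arms in baseline, a misfitted slope no longer cancels out of the contrast.

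**Working it through.** **Inputs from the documents.** Post-baseline visits to Week 24 are Weeks 4, 8, 12, 18 and 24 for AAPPO and SALT (5 visits) and Weeks 4, 8, 12 and 24 for HADS (4 visits). About 660 subjects are planned in six groups to Week 24, with placebo pooled. No SD, correlation or power is stated for any continuous endpoint, so there is no plan figure to reproduce and the correlations below are assumptions.

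**Precision: formulas.** Take baseline SD = 1.

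- Slope of change on baseline at visit t: b_t = r_t × SD_t − 1, where r_t is the correlation with baseline.
- Common slope: b_c = (1′V⁻¹b)/(1′V⁻¹1), with V = C + (b − b_c)(b − b_c)′ solved to a fixed point. C is the residual covariance given baseline.
- Week 24 variance ratio, shared slope against visit-specific slopes: 1 + (b_24 − b_c)²/C_24.

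**Assumed correlations.** Correlation between two visits = a × ρ^(weeks apart/4), with a from 0.75 to 0.90 and ρ from 0.90 to 0.97.

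- Week 4 correlation with baseline runs from 0.75 × 0.90 = 0.68 to 0.90 × 0.97 = 0.87.
- Week 24 correlation with baseline runs from 0.75 × 0.90⁶ = 0.40 to 0.90 × 0.97⁶ = 0.75.

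**The two extremes, AAPPO visits, equal SDs:**

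| a, ρ | r at Wk 4 → Wk 24 | b_24 | b_c | C_24 = 1 − r_24² | Variance ratio |
|---|---|---|---|---|---|
| 0.75, 0.97 | 0.73 → 0.62 | −0.375 | −0.3105 | 0.610 | 1 + 0.0042/0.610 = 1.007 |
| 0.90, 0.90 | 0.81 → 0.48 | −0.522 | −0.272 | 0.771 | 1 + 0.0625/0.771 = 1.081 |

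With the HADS visits the range is 1.008 to 1.082. On the SE scale this is √1.007 = 1.003 to √1.082 = 1.040. A contrast with 80% power under visit-specific slopes would, at the upper end, have (1.96 + 0.84)/1.04 − 1.96 = 0.73, or about 77%.

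**If the SD grows.** With SD 20% larger at Week 24, the second case has b_24 = 0.478 × 1.2 − 1 = −0.426, closer to the early slopes. The range becomes 1.000 to 1.043. With 30% growth it is about 1.001 to 1.029.

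**Other assumed patterns, as SE ratios:**

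- Constant correlation 0.6, equal SDs: 1.000.
- Fall from 0.7 to 0.5: 1.012.
- Fall from 0.8 to 0.4: 1.058-1.084 with equal SDs, 1.03-1.05 with SD growth of 20%.
- Deliberately steep fall from 0.8 to 0.3: 1.22.

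The size follows the assumed drift.

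**Cost of the term.** It needs 5 − 1 = 4 extra slopes (AAPPO, SALT) or 4 − 1 = 3 (HADS). If slopes are truly equal, estimating a slope adds at most about 1/(660 − 6 − 2) = 0.15% to the variance, or 0.08% to the SE.

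**Bias, same dropout mechanism in every arm.** 200 simulated trials per scenario, N = 660, 10-12% MAR dropout driven by the last observed value, true Week 24 effect −0.30:

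| Baseline correlation | Shared slope | Baseline-by-visit | Model SE ratio |
|---|---|---|---|
| 0.6 throughout | −0.309 | −0.309 | 1.000 |
| 0.7 → 0.5 | −0.301 | −0.302 | 1.012 |
| 0.8 → 0.4 | −0.311 | −0.307 | 1.082 |

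There is essentially no difference in the estimates, and the SE ratios agree with the formula.

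**Bias, dropout driven by baseline and differing by arm.** Two arms, 240 subjects, dropout after Week 8, baseline correlation falling from about 0.77-0.79 to 0.45-0.55, true effect −0.30:

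- Placebo-only dropout (17-18% overall): shared slope −0.339 and −0.346; baseline-by-visit −0.302 and −0.301.
- Dropout in opposite directions by arm (18-20%, deliberately adverse): shared slope −0.372 and −0.405; baseline-by-visit −0.298 and −0.310.

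A separate simulation with 16-19% arm-differential dropout gave about −0.37 against −0.30. Baseline-driven dropout that was the same in both arms gave no bias.

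**The case against.** The strongest reply is that the plan prespecifies a valid, common model and that the gain is unknown and may be nil. Much of this stands.

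- A reader might infer that the questionnaires do lose precision, or that Week 24 is adjusted with the wrong slope. The documents do not support either statement. They contain no SD, correlation or slope for AAPPO or HADS, and the sample size rests on binary endpoints. Falling correlation alone is not enough, because growth in SD offsets it.
- A reader might infer that the model is biased. Randomisation and the unstructured covariance protect the contrast when dropout is similar across arms: the misfit goes into the Week 24 residual variance and the SE stays honest. The bias needs dropout that depends on baseline and differs by arm, and the documents give no dropout rate by arm.
- A reader might call the term free. It costs 3-4 parameters, and if slopes are equal it recovers nothing.
- The stakes are limited. These endpoints are tested at an unadjusted 5%, outside the Type I error procedure. For change in SALT score, one simulated example showed a gain close to 0.

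What does not stand is the conclusion that nothing should change. The possible loss is several percent of variance against about 0.08% of the SE, and the unqualified MAR claim in SAP 5.3.2 depends on a mean model that has not been secured.

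**Conclusion.** The point holds in conditional form, as a minor improvement. As specified, one baseline slope is shared across visits for every change-from-baseline endpoint that uses this MMRM.

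- **Precision:** about 1-8% in Week 24 variance under the assumed serial correlations with equal SDs, 0-4% if the SD grows 20%, and zero if slopes are equal. A steeper drift would cost more. Which case applies cannot be settled from the documents.
- **Bias:** essentially none with similar dropout across arms. With MAR dropout that depends on baseline and differs by arm, the shared slope moved a true −0.30 to between about −0.34 and −0.41 in the simulated patterns, while the interaction model stayed near −0.30. In these patterns the shift overstated benefit. Its sign in practice depends on which arm loses which subjects.

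It should not be read as a threat to the trial's main conclusions: no primary, key secondary or alpha-controlled analysis uses this model.

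**What to change.** Before unblinding, add a baseline-by-visit interaction to the MMRM in SAP 5.2.3 for all change-from-baseline endpoints (SALT score, AAPPO Emotional Symptoms and Activity Limitations, HADS depression and anxiety). Qualify the sentence in SAP 5.3.2 so that unbiasedness under MAR is tied to a correctly specified mean model.

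The cost is 4 parameters for AAPPO and SALT and 3 for HADS to Week 24, with no new data. SAP 5.2.3 also fits the MMRM to Week 48 in the initially active arms. There the count is visits minus one: 8 for SALT (9 visits), 7 for AAPPO (8 visits) and 4 for HADS (5 visits), still small.

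A SAP edit is enough. Protocol section 9 lets the SAP modify the protocol's methods and requires an amendment only for major changes to the primary endpoint definitions or their analyses. Protocol 9.2.3 can be aligned at the next amendment, if there is one.

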5.3. Methods to Manage Missing Data

In general, for analyses using descriptive statistics, missing values will not be imputed. Missing values for exploratory endpoints will not be imputed unless specified otherwise. In addition, for safety endpoints, missing values will not be imputed. Other methods for handling missing values are discussed below.

5.3.1. Binary Endpoints

The same rule will be used for any missing data whether it is a missed visit, or it is a missing value due to early discontinuation. Depending on the analysis and the endpoint being analyzed, the following approaches will be used for managing missing data in binary endpoints:

- a. Subjects with missing SALT scores due to COVID-19 in a given visit will be excluded from the analysis at that timepoint, whereas subjects with missing SALT scores due to other reasons will be treated as non-responders at that timepoint (Analysis 1, [Section 5.2.1.1](#)).
- b. Subjects with missing SALT scores due to any reason in a given visit will be treated as non-responders at that timepoint (Analysis 3, [Section 5.2.1.1](#)).
- c. Imputation of missing SALT response at Week 24 is performed based on the predictive distribution of the GLMM under MAR (Analysis 2, [Section 5.2.1.2](#)).

- d. Imputation of missing SALT response at Week 24 is performed based on the predictive distribution of the GLMM under MNAR using tipping point analysis (Analysis 2a, [Section 5.2.1.2](#)).
- e. Imputation of missing SALT response is performed based on the predictive distribution of the GLMM under MAR for subjects with missing data due to COVID-19, whereas subjects with missing SALT scores due to other reasons will be treated as non-responders at that timepoint (Analysis 4, [Section 5.2.1.3](#)).
- f. Imputation of missing SALT response is performed based on the predictive distribution of the GLMM under MNAR using tipping point analysis for patients with missing data due to COVID-19, whereas subjects with missing SALT scores due to other reasons will be treated as non-responders at that timepoint (Analysis 4a, [Section 5.2.1.3](#)).

5.3.2. Continuous Endpoints

For continuous endpoints such as absolute SALT score or change from baseline in SALT score measured longitudinally, missing values post-baseline will not be imputed. For longitudinal continuous endpoints, assuming that the missing data mechanism is MAR, the data will be analyzed based on the full likelihood using a linear mixed-effect model with repeated measures for these continuous variables (see [Section 5.2.3](#)). This model will yield unbiased estimates and valid inferences in the presence of a missing data mechanism that is MAR.

For the continuous PRO variables such as AAPPO, HADS, EQ-5D-5L/EQ-5D-Y, SF-36v2, and WPAI:AA, rules suggested by Pfizer (for AAPPO) or the developers of these instruments will be followed in calculating the missing item-level and scale values. If these rules are not enough for imputing a value, then the missing values will be handled in the same way as efficacy variables.

6. ANALYSES AND SUMMARIES

Analysis will be done by testing the difference between each of the PF-06651600 QD-treated groups and placebo for the first 24 weeks. For the 25-48 week period, point estimates of the PF-06651600 QD-treated groups and the associated 95% CIs will be presented without testing any hypotheses.

Visit windows to be used for all efficacy analyses and some relevant safety analyses are detailed in [Section 9.1](#).

The analyses of the primary endpoint(s) are described separately for the overall study and for specific regulatory regions in order to address differences in advice received from some regulatory agencies.

6.1. Primary Endpoints, Key Secondary and α -controlled Endpoints

Since this **CCI** supports submission in several regions with different regulatory requirements the analyses of some endpoints may overlap to support multiple regions with different designations. This section describes the analyses planned for endpoints

that are either primary, key secondary or α -controlled endpoints for the overall study reporting or for at least one of the known regional regulatory requirement.

6.1.1. Response Based on SALT Score ≤ 20 at Week 24

- Response based on SALT Score ≤ 20 at Week 24
- Population: FAS
- Statistical methods:
 - Analysis 1, [Section 5.2.1.1](#) – this is the primary analysis and primary endpoint for the study and for the FDA/PMDA. This analysis will be repeated in the PPAS. This method will be also used for the analysis of earlier timepoints.
 - Analyses 2 and 2a, [Section 5.2.1.2](#) – this is a supplementary analysis for the study and for the FDA/PMDA
 - Analysis 3, [Section 5.2.1.1](#) – this is a supplementary analysis for the study, for the FDA/PMDA, and for the EMA and competent authorities in the VHP countries.
 - Analysis 4, [Section 5.2.1.3](#) – this is an α -controlled analysis for the EMA and competent authorities in the VHP countries.

6.1.2. Response Based on SALT Score ≤ 10 at Week 24

- Response based on SALT Score ≤ 10 at Week 24
- Population: FAS
- Statistical methods:
 - Analysis 4, [Section 5.2.1.3](#) – this is the primary analysis and primary endpoint for the EMA and competent authorities in the VHP countries. This analysis will be repeated in the PPAS. This method will be also used for the analysis of earlier timepoints. This analysis could also be considered as supplementary for the overall study.
 - Analysis 1, [Section 5.2.1.1](#) – this is the key secondary endpoint for the study, and considered a supplementary analysis for the EMA and competent authorities in the VHP countries. For the FDA/PMDA this is an α -controlled analysis. This analysis will be repeated in the PPAS.
 - Analysis 3, [Section 5.2.1.1](#) – this is considered a supplementary analysis for the study and for the EMA and competent authorities in the VHP countries.

- Analysis 4a, [Section 5.2.1.3](#) – this analysis is supplementary for the EMA and competent authorities in the VHP countries.

6.1.3. PGI-C Response at Week 24

- PGI-C response at Week 24
- PGI-C response is defined as PGI-C score of “moderately improved” or “greatly improved” at Weeks 4, 8, 12, 18, 24, 34, 40, and 48.
- Population: FAS
- Statistical methods:
 - Analysis 4, [Section 5.2.1.3](#) – this is the key secondary endpoint for the EMA and competent authorities in the VHP countries. This analysis will be repeated in the PPAS.
 - [Section 6.2.9](#) describes other analysis that will be conducted for the PGI-C as a secondary endpoint the overall study and for the FDA/PMDA.

6.2. Secondary Endpoints

The analysis of binary secondary endpoints in the placebo-controlled phase will use the same approach in Analysis 1 ([Section 5.2.1.1](#)).

6.2.1. Exposure Response for Response Based on SALT Score ≤ 20 at Week 24

- Response based on SALT Score ≤ 20 at Week 24.
- Population: FAS.
- Statistical Method: Bayesian three-parameter E_{\max} model with the log odds (logit) of the probability of response based on SALT score ≤ 20 at Week 24 ([Section 5.2.2](#)).
- Missing Data: Exclude missing due to COVID-19, consider missing due to other as non-responders.

6.2.2. Exposure Response for Response Based on SALT Score ≤ 10 at Week 24

- Response based on SALT Score ≤ 10 at Week 24.
- Population: FAS.
- Statistical Method: Bayesian three-parameter E_{\max} model with the log odds (logit) of the probability of response based on SALT score ≤ 10 at Week 24 ([Section 5.2.2](#)).
- Missing Data: Exclude missing due to COVID-19, consider missing due to other as non-responders.

6.2.3. Response Based on SALT Score ≤ 20 at all Visits

- Response based on SALT Score ≤ 20 at all visits except Week 24.
- Population: FAS.
- Statistical Method: MN up to week 24. Descriptive method for entire duration.
- Missing Data: Exclude missing due to COVID-19, consider missing due to other as non-responders.

6.2.4. Response Based on SALT Score ≤ 10 at all Visits

- Response based on an absolute SALT Score ≤ 10 at Weeks 4, 8, 12, 18, 24, 28, 34, 40, and 48.
- Population: FAS.
- Statistical Method: MN up to week 24. Descriptive method for entire duration.
- Missing Data: Exclude missing due to COVID-19, consider missing due to other as non-responders.

6.2.5. 75% Improvement in SALT Score (SALT75)

- Response based on a 75% improvement in SALT score from baseline (SALT75) at Weeks 4, 8, 12, 18, 24, 28, 34, 40, and 48.
- Population: FAS.
- Statistical Method: MN up to week 24. Descriptive method for entire duration
- Missing Data: Exclude missing due to COVID-19, consider missing due to other as non-responders.

